Official Title:

Effect of different labor analgesics on maternal UtA, fetal UA and MCA blood flow index observed by Doppler ultrasonography: A prospective randomized double-blinded controlled trial

Document Date:

March 1, 2021

Study protocol

1. Study design

Pregnant women of ASA grade I to II, aged 20 to 35 years, weighing 50 to 100 kg, 150-175 cm in height, and 37 to 41 weeks of gestation were included in the study. Women with contraindications of spinal anesthesia, maternal complications (such as pregnancy-induced hypertension, preeclampsia, cardiovascular and cerebrovascular diseases, etc.), abnormal uterine contractions, abnormal placental function or position, signs of fetal distress, and known fetal malformations were excluded. The patients who were failed to administer combined spinal and epidural block analgesia, those who were transferred from vaginal trial labor to cesarean section, those who could not cooperate with ultrasound detection, and those who needed to use oxytocin were excluded. The study was planned and implemented in accordance with the Declaration of Helsinki.

2. Randomization and blinding

90 parturients in the study were randomly assigned to Sufentanil group (S, n=30), Ropivacaine group (R, n=30) and Sufentanil added to Ropivacaine group (SR, n=30) by non-blind personnel according to the computer random number table, and the allocation was hidden. The solution was prepared by an unblinded anesthesiologist and packaged in a blind way and administered by another anesthesiologist. The patients, anesthesia providers, data recorders, ultrasound examiners, obstetrical staff, and nursing staff remained blinded to group assignment throughout the study.

3. Study intervention

At the time of request for labor analgesia, patients were randomized to receive either sufentanil 5 µg (Group S), ropivacaine 3mg (Group R), or sufentanil 2.5 µg added to ropivacaine 2.5 mg (Group SR) into the subarachnoid space. All groups received the standard epidural solution that contained 0.1% ropivacaine with 0.25 µg/ml sufentanil. Routine obstetric and anaesthetic monitoring was given after maternal entered the delivery room.

An experienced the anesthesiologist select L3-4 lumbar vertebra clearance to puncture with standard sterile technique using loss of resistance when the puerpera palace has expanded to about 3 cm. After the puncture reached the epidural space, a 25-gauge lumbar anesthesia needle was used to puncture into the subarachnoid space. 2 mL of anesthetic drug as determined by her group randomization were administered into the cavity through the lumbar anesthesia needle after cerebrospinal fluid flow out. A 19-gauge spring-wound catheter was threaded 4-6 cm into the epidural space. All patients received a test dose of 3 ml of 1.5% lidocaine followed by an initial loading dose of 5 ml of the standard epidural solution. Epidural catheters into vessels or subarachnoid space were excluded. An analgesic pump (PCEA pump, 100ml) containing standard epidural solution was then connected to the epidural catheter at a background continuous infusion rate of 5 mL/h. The visual analogue score for pain (VAS) was performed 15 minutes after the injection dose, and if the VAS score fell below 3, the case was included in the study.

An anesthesia provider assessed the adequacy of analgesia for the patients throughout the duration of labor. Any breakthrough pain was managed with a physician-administered epidural bolus. All obstetric analgesia procedures were performed by the same anesthesiologist to reduce errors due to technical reasons.

4. Ultrasonic examination method

The patients were placed in a supine position with calm breathing to perform doppler ultrasonography during the interval of contractions. Ultrasound probe was

placed on fetal head area. Middle cerebral arteries (MCA) run anteriorly on both sides of the ring of cerebral arteries at the position of the double head diameter (see Figure 1A). We can get waveforms of MCA examined by pulsed wave doppler (see Figure 1B). The probe was placed at the placenta area, and we can see the fetal umbilical cord connecting to the center of the placenta. Umbilical artery (UA) could be identified by color flow, and its waveforms were examined by pulsed wave doppler (see Figure 1C and 1D). The probe was placed at the midpoint of the groin. The right and left uterine arteries (UtA) could be identified by color flow at the apparent crossover with the external iliac arteries, and pulsed wave doppler was used to obtain waveforms (see Figure 1E and 1F). 3 to 10 arterial spectrograms with clear edges and no background noise at baseline were selected. The above arterial blood flow indexes were measured three times and the average value was taken. The S/D、PI、RI value of MCA、UA、UtA can be measured automatically by ultrasound instrument. All doppler examinations were performed by the same sonographer.

5. Primary outcomes

The main indexes were doppler blood flow indexes (S/D, PI, RI value) of UtA, UA, MCA before analgesia (T_0) and 30 min (T_1), 60min (T_2), 90 min (T_3) after analgesia in the three groups.

6. Secondary outcomes

Fetal heart rate (FHR) and mean artery pressure (MAP) at T_0 , T_1 , T_2 and T_3 , neonatal weight, time of each stage of labor, rate of midwifery, neonatal umbilical artery blood gas index and Apgar score at 1 min, 5 min, 10 min after birth of the three groups were included in the secondary indicators.

7. Statistical Analysis Plan

In this study, SPSS 13.0 was used for statistical analysis, and GraphPad Prism 8 was used for mapping. Measurement data were expressed as mean \pm standard deviation ($\bar{x}\pm s$), and categorical data were expressed as frequency, percentage, or rate. Paired t

test was used for intra-group comparison and independent sample t test was used for inter-group comparison of measurement data conforming to normal distribution. The measurement data with non-normal distribution were analyzed by rank sum test. Chi-square test was used for statistical analysis of categorical data. $P < 0.05$ indicates statistical significance.

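### Parity is absent from entry, allocation and analysis, so the comparisons of labour-stage times are less precise than they could be, though not biased

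*Combined protocol and SAP*

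**What the plan says.** Section 1 (Study design) limits entry to ASA grade I to II women "aged 20 to 35 years, weighing 50 to 100 kg, 150-175 cm in height, and 37 to 41 weeks of gestation were included". The exclusions cover contraindications to spinal anaesthesia, maternal complications and "abnormal uterine contractions, abnormal placental function or position, signs of fetal distress, and known fetal malformations were excluded". None of these criteria mentions parity, so nulliparous and parous women are both eligible.

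Section 2 (Randomization and blinding) assigns 90 women, 30 to each of three arms, "by non-blind personnel according to the computer random number table, and the allocation was hidden". It describes no strata, blocks or minimisation.

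Section 6 (Secondary outcomes) lists, among other items, "neonatal weight, time of each stage of labor, rate of midwifery". The last of these is read here as the assisted-delivery rate.

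Section 7 (Statistical Analysis Plan) states that "independent sample t test was used for inter-group comparison of measurement data conforming to normal distribution", sends non-normal measurements to a rank sum test, and adds that "Chi-square test was used for statistical analysis of categorical data". No covariate appears in any analysis.

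**The concern.** Parity is fixed before allocation and belongs to the routine obstetric history. On the ordinary assumption that first labours run longer, it is a leading baseline predictor of labour-stage times. The plan narrows height and weight but does not use parity in eligibility, allocation or analysis. Whatever part of the spread in labour times is due to parity is therefore counted as random error in each between-arm test.

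What is at stake is the precision of some secondary comparisons. With 30 women per arm, and no effect size, SD or power stated, the plan shows no margin to absorb an avoidable loss.

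**Working it through.** **The plan's own figure.** Three arms of 30 make 90. No effect size, SD or power is given, so there is no power calculation to reproduce.

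**Inputs.**
- From the documents: n = 30 per arm (Section 2); significance at P < 0.05 (Section 7), taken as two-sided.
- Assumed: nulliparous share p = 0.5 to 0.7; parity gap D = 0.5 to 2, in within-parity SDs of labour time.

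**Precision.** Set the within-parity variance to 1. The variance faced by an unadjusted test is v = 1 + p(1−p)D². Adjusting for parity multiplies the SE by 1/√v.

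With parity controlled, the difference detectable with 80% power is (1.960 + 0.842) × √(2/30) = 0.723 within-parity SD. Unadjusted power for that same difference is Φ(2.802/√v − 1.960). The number per arm that the unadjusted test would need to match is 30v, rounded up. Each cell gives p = 0.5, then p = 0.7.

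| D | v | SE ratio 1/√v | SE reduction forgone | Unadjusted power | n per arm to match |
|---|---|---|---|---|---|
| 0.5 | 1.0625; 1.0525 | 0.970; 0.975 | 3.0%; 2.5% | 78%; 78% | 32; 32 |
| 1 | 1.25; 1.21 | 0.894; 0.909 | 11%; 9% | 71%; 72% | 38; 37 |
| 1.5 | 1.5625; 1.4725 | 0.800; 0.824 | 20%; 18% | 61%; 64% | 47; 45 |
| 2 | 2.00; 1.84 | 0.707; 0.737 | 29%; 26% | 51%; 54% | 60; 56 |

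The formula assumes a linear model with common variance. It ignores the small cost of estimating one more coefficient, which would eat into the gain at D = 0.5.

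**Chance imbalance.** The SD of the difference in nulliparous share between two arms is √(2p(1−p)/30) = 0.129 at p = 0.5 and 0.118 at p = 0.7, or 12 to 13 points. A gap of at least 20 points has probability 12% to 16% for a given pair of arms (exact binomial). For the widest gap among the three arms it is 27% to 33% (simulated).

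A 20-point gap shifts a mean difference by 0.2D. The unadjusted SE is √(2/30) × √v = 0.258√v. For p = 0.7 to 0.5:
- D = 1: shift 0.20 against SE 0.28 to 0.29.
- D = 1.5: shift 0.30 against SE 0.31 to 0.32.
- D = 2: shift 0.40 against SE 0.35 to 0.37.

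The shift is below one SE up to D = 1.5 and slightly above one at D = 2. In every case it is well short of the 1.96 SE needed for significance on its own.

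**Type I error.** In 40,000 simulated unadjusted t tests with D = 1, p = 0.5 and no drug effect, 4.8% were significant.

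**Assisted delivery.** With assumed rates of 15% v 3%, or 25% v 5%, in first v repeat births and p = 0.5, a 20-point gap shifts the risk difference by 0.2 × 12 = 2.4 or 0.2 × 20 = 4.0 points. The SEs are 7.4 and 9.2 points, so the effect is small.

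**The case against.** The strongest reply is that this touches only secondary outcomes and that randomisation already deals with parity. Both parts are correct. The comparison is unbiased, and the ordinary SE already allows for chance differences in parity. A reader might infer that an unlucky split could pass for a drug effect. The unadjusted test keeps its error rate, and a 20-point gap cannot by itself produce significance over the assumed range. Imbalance and a larger error term are also largely the same variance described twice.

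A reader might further infer that parity imbalance decides who reaches the 90-minute scan. The documents give no figure for delivery within 90 minutes, overall or by parity, so they do not support that. Nor do they show any effect of parity on the Doppler indices.

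The size of the gain is also open to challenge. Neither p nor D is in the documents, D need not be the same for each stage of labour, and excluding caesarean and oxytocin cases may change the parity gap among the women analysed. This stands: the gain could be trivial.

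Finally, stratified lists may be the wrong tool. Section 1 removes women for failed block, caesarean or oxytocin, and Section 3 keeps only those with a VAS below 3 at 15 minutes after the injection. Balance achieved at allocation can be lost by the time of analysis, and stratification followed by unadjusted tests does not give the full gain. This also stands, and it is why adjustment comes first in the fix.

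What the reply does not answer is that the planned test leaves out a known baseline predictor that costs almost nothing to include. The absence of stratification is read from silence, but nothing in the text contradicts it.

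**Conclusion.** The point holds as a loss of precision in the labour-stage comparisons. At p = 0.5 to 0.7, the SE reduction forgone is about 3% at a parity gap of 0.5 SD, 9% to 11% at 1 SD and 26% to 29% at 2 SD. It is worth having only if parity separates labour times by about 1 SD or more, which is an assumption. Validity is not in question, and the point does not extend to the primary outcomes, to attendance at the 90-minute scan, or to a material gain for assisted delivery.

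**What to change.** Record parity (nulliparous or parous) for every woman before allocation. In Section 7, prespecify it as a factor in the between-arm comparison of the time of each stage of labour. Use a linear model with arm and parity, on log time if the times are skewed, or a parity-stratified rank test (van Elteren), in place of the unadjusted t or rank sum test. The cost is one baseline field and one model term; no more women are needed and eligibility is unchanged. If enrolment has begun, this can still be specified before unblinding, provided parity can be taken from the obstetric record.

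If enrolment has not begun, separate blocked 1:1:1 lists for nulliparous and parous women are an optional addition. They mean a little more list handling for the unblinded person, and arm totals may not come to exactly 30. They do not replace the adjustment.

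### Women in whom the combined spinal-epidural fails are excluded after randomisation, some of them after receiving the allocated spinal drug, and no analysis set keeps them in their arm

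*Combined protocol and SAP*

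**What the plan says.** The relevant statements are spread over four sections of the combined protocol and SAP.

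- **Timing of randomisation (section 3):** "At the time of request for labor analgesia, patients were randomized to receive either" one of the three spinal solutions.
- **Order of the block (section 3):** the epidural space is reached, the spinal needle is passed, and once cerebrospinal fluid (CSF) is seen, "2 mL of anesthetic drug as determined by her group randomization were administered into the cavity". The epidural catheter and the test dose come only after that. All arms share one epidural solution, so the spinal dose is the only treatment that differs.
- **Exclusion for a failed block (section 1):** "The patients who were failed to administer combined spinal and epidural block analgesia" are excluded. The same sentence also excludes "those who were transferred from vaginal trial labor to cesarean section, those who could not cooperate with ultrasound detection" and women who need oxytocin.
- **Two further steps after the spinal dose (section 3):** "Epidural catheters into vessels or subarachnoid space were excluded", and a case counts as included only if the pain score is below 3 at 15 minutes.
- **Numbers (section 2):** "90 parturients in the study were randomly assigned", 30 to each arm.
- **Analysis (section 7):** tests are named, but there is no analysis set, replacement rule or allowance for losses.

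**The concern.** An exclusion applied before randomisation only narrows the population. One applied after randomisation can undo the balance that randomisation provides, most clearly when it follows the allocated treatment. The section 1 rule reads like an eligibility criterion, but in the section 3 sequence it can only act on women already randomised. It mixes two kinds of failure:

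- **Before injection.** No CSF is obtained and no allocated drug is given. Staff performing the block are blinded, so failure should not depend on the arm. The cost is numbers.
- **After injection.** The spinal dose is in, but the catheter cannot be placed or is misplaced. The woman has had the treatment under study, and removing her takes a treated participant out of her randomised arm.

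Two things are at stake: whether the Doppler comparison is between the groups as randomised, and how many women per arm are analysed.

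**Working it through.** **Sequence.** Setting sections 1 and 3 side by side gives this order: request and randomisation; epidural puncture at about 3 cm dilatation; spinal needle and CSF; allocated 2 mL; catheter; test dose; loading dose; pain score at 15 minutes. Failure of the combined block can occur from the puncture onwards, always after randomisation. Failure of the epidural part can be found after the allocated 2 mL is given. Nothing in section 7 brings such women back into the analysis.

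**The plan's own figure.** The 30 per arm cannot be reproduced, because no effect size, SD, power or loss rate is given. What follows is sensitivity only.

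**Inputs.** From the plan: 30 per arm, 90 in total, an independent-sample t test and significance at P < 0.05 (taken as two-sided, which the plan does not state). Assumed: a failure rate f of 2% to 10%, covering both kinds of failure, since the documents give none.

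**If 90 is the number randomised and nobody is replaced:**

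- Lost per arm = 30f: 30 × 0.02 = 0.6, and 30 × 0.10 = 3. Over 90 women, 1.8 to 9.
- Expected analysed per arm = 30(1 − f): 29.4 at 2%, 28.5 at 5%, 27.0 at 10%.
- Chance that all 90 are kept = (1 − f)^90: 16% at 2%, 1.0% at 5%, about 0.01% at 10%.
- 95% half-width for a difference between two arms, in SD units = t(0.975, 2n − 2) × √(2/n): 0.517 at n = 30, 0.536 at n = 28, 0.546 at n = 27. The ratio 0.546/0.517 = 1.056, about 6% wider.
- Power, normal approximation, for the difference that gives 80% with 30 per arm, (1.960 + 0.842) × √(2/30) = 0.723 SD: 79.2% at 2%, 78.0% at 5%, 75.7% at 10%.

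**If 90 is the number left after exclusions:** 90/(1 − f) women were randomised, which is 91.8 at 2% and 100 at 10%. About 2 to 10 randomised women then have no place in the plan's numbers.

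**Bias, as an extreme illustration.** If 3 of 30 are removed in one arm only and differ from the other 27 by 1 SD, that arm's mean moves by 3/30 = 0.10 SD, about one fifth of the 0.517 SD half-width. This requires the whole assumed 10% to fail after injection, in one arm only, with a full 1 SD difference. The documents support none of these.

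**The case against.** The strongest reply is that failure of the block is mainly technical. One anesthesiologist performs every procedure, expressly to limit technical error, and staff are blinded. Failure at a few percent costs about one or two points of power. All of this stands, and it is why the point is modest.

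Several stronger readings are tempting, but the documents do not support them:

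- **That 30 per arm is not delivered.** This requires 90 to be the number randomised, at least one exclusion, and no replacement. Because section 3 counts a case as included only after the pain score, 90 may instead be the number left. No power target is given, so no required number is shown to be missed. What can be said is that the analysed number is undefined.
- **That detection of catheter misplacement depends on the arm.** One might argue that the test dose is read on top of different spinal drugs. The plan does not say how misplacement is detected, so this is inference. The catheter sentence may also mean only that misplacement was ruled out. The section 1 exclusion stands either way.
- **That further women are lost between request and puncture, or that the T0 scan follows randomisation.** The plan gives dilatation at puncture, not at request, and places T0 only before analgesia.

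It is also fair to say that the pain-score, caesarean and oxytocin exclusions could depend more on the allocated drug than a failed block does. They may be the larger threat to the comparison. They are separate rules and do not make this one sound.

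**Conclusion.** The point holds in a limited form. The order of events in section 3 and the exclusion in section 1 together remove randomised women. Where the epidural part fails after the spinal injection, they remove women already given the treatment being compared. No analysis set corrects this. That conclusion rests on the text alone.

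The size rests on the assumed 2% to 10% failure rate and, for the loss of precision, on 90 being the number randomised without replacement. On those terms the confidence interval is at most about 6% wider. Bias is possible only through failures after injection. Its direction and size depend on how failure relates to arm, which the documents do not show, and the 0.10 SD illustration is an extreme case, not an estimate. The change is worth making because it is cheap and protects the randomised comparison, not because a large distortion has been shown.

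**What to change.** 1. Change section 1 so that every woman who received the allocated spinal dose stays in her randomised arm for all between-arm analyses, with T1 to T3 scans obtained where possible. State that neither the catheter exclusion nor the pain-score condition in section 3 removes her from this set. Analyse without such women only as a sensitivity analysis.
2. Randomise as late as practical: at block set-up, after the T0 scan. If the puncture fails before injection, report the woman as randomised but not treated, log the unused syringe and do not reuse her allocation. Her allocation has been drawn, so she should not be relabelled as a pre-randomisation exclusion.
3. State that 30 per arm is the number randomised, and report the numbers randomised, dosed and analysed in each arm.

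This is mainly protocol wording, with no change to treatment. The costs are syringes prepared at shorter notice and occasionally discarded, and slight noise from a few women without the standard epidural. Some dosed women may still lack later scans, and these should be counted as missing data by arm. Fixing 30 as the number randomised accepts the small loss of precision from failures before injection, and the other exclusions in section 1 can still reduce the number analysed.

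### The caesarean exclusion has no time limit, so randomised women with complete Doppler data can be dropped and neonatal and labour outcomes compared only among vaginal births; the oxytocin exclusion is also untimed

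*Combined protocol and SAP*

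**What the plan says.** Section 1 first lists ordinary entry exclusions (maternal disease, abnormal contractions, fetal distress and similar). A separate sentence then adds four more:

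- failed block: "The patients who were failed to administer combined spinal and epidural block analgesia";
- caesarean: "those who were transferred from vaginal trial labor to cesarean section";
- inability to cooperate with ultrasound;
- oxytocin: "those who needed to use oxytocin were excluded".

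None of the four has a time point.

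Section 2 says that "90 parturients in the study were randomly assigned", 30 to each of three groups. Section 3 sets the moment: "At the time of request for labor analgesia, patients were randomized". The puncture is made "when the puerpera palace has expanded to about 3 cm". Two further conditions in Section 3 apply after that point: "Epidural catheters into vessels or subarachnoid space were excluded", and, for the pain score 15 minutes after injection, "if the VAS score fell below 3, the case was included in the study".

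Section 5 ends the primary Doppler measurements at T3, 90 minutes after analgesia. Section 6 lists birth weight, duration of each stage of labour, the midwifery rate, cord gases and Apgar scores. It lists neither caesarean nor oxytocin use. Section 7 names tests and a significance level, but no analysis set, replacement rule or handling of missing data.

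**The concern.** A conversion to caesarean before the analgesia request is an ordinary entry exclusion. A conversion in a woman already randomised is a post-randomisation event, and one after T3 removes a woman whose primary data are complete.

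Caesarean and oxytocin use could depend on the allocated drug, through fetal heart rate changes or slower labour. If so, the women left in each arm are no longer comparable by randomisation. The delivery and neonatal outcomes are the most exposed. If one arm had more caesareans for fetal compromise, those babies would leave its Apgar and cord-gas results and the arm would look better for it. Since caesarean and oxytocin use are not outcomes, a reader of the results might not be able to see this.

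For the primary Doppler outcome the cost is lost usable data and a bias of unknown size.

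**Working it through.** **Timing.** The order of events is randomisation (analgesia request), puncture at about 3 cm, pain score at 15 minutes, scans to 90 minutes, the rest of labour, birth. Much of labour, and so much of the opportunity for caesarean or oxytocin, follows randomisation. The exclusions cannot be read as entry criteria only: their sentence opens with failed block, normally known only after randomisation, and the pain-score condition shows that the plan selects women after dosing.

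**The plan's own figure.** Only 3 × 30 = 90 can be reproduced. No effect size, SD, power, loss rate, caesarean rate or oxytocin rate is given. Everything below is an illustration under assumptions.

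**1. Precision**, if 90 is the number randomised and nobody is replaced. Two-sample t test, two-sided 0.05, noncentral t; 80% power at 30 per arm is a benchmark chosen here.

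| Lost | Left per arm | Detectable difference, 80% power (SD) | Power for 0.736 SD |
|---|---|---|---|
| 0% | 30 | 0.736 | 80% |
| 10% | 27 | 0.777 | 76% |
| 20% | 24 | 0.826 | 70% |
| 30% | 21 | 0.886 | 64% |
| 40% | 18 | 0.961 | 57% |

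The normal approximation √(2/30) × (1.960 + 0.842) gives 0.72 SD at 30 per arm, which agrees. If excluded women are replaced, this loss disappears but the selection remains.

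**2. False difference when there is no true one.** Let Y be a standard normal neonatal outcome (higher is better). A woman is excluded when −ρY + √(1−ρ²)e exceeds a threshold, with e standard normal. If a proportion p is excluded, the retained mean rises by ρ·φ(z)/(1−p), where z is the upper-p normal quantile and φ the normal density.

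- p = 10%: 0.1755/0.9 = 0.195
- p = 20%: 0.2800/0.8 = 0.350
- p = 30%: 0.3477/0.7 = 0.497

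The false difference is ρ × (0.350 − 0.195) = ρ × 0.155 for 10% against 20%, and ρ × (0.497 − 0.195) = ρ × 0.302 for 10% against 30%. The error rates come from 40,000 simulated trials per setting, with 30 randomised per arm and no replacement.

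| Exclusion rates | ρ = 0.3 | ρ = 0.5 | ρ = 0.7 |
|---|---|---|---|
| 10% v 10% | 0; 5% | 0; 5% | 0; 5% |
| 10% v 20% | 0.05 SD; about 5% | 0.08 SD; about 6% | 0.11 SD; about 7% |
| 10% v 30% | 0.09 SD; about 6% | 0.15 SD; about 8% | 0.21 SD; about 12% |

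**3. Masking of a true harm of 0.50 SD**, with the same threshold c in both arms. The harmed arm then loses 1 − Φ(c − 0.5ρ). The difference seen is 0.50 + ρ[λ(c) − λ(c − 0.5ρ)], with λ(x) = φ(x)/Φ(x). For example, with ρ = 0.5 and 10% excluded in the comparator, c = 1.2816 and c − 0.25 = 1.0316, so 0.50 + 0.5 × (0.195 − 0.276) = 0.46 SD.

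| For ρ = 0.3 / 0.5 / 0.7 | Comparator loses 10% | Comparator loses 20% |
|---|---|---|
| Harmed arm loses | 12.9 / 15.1 / 17.6% | 24.5 / 27.7 / 31.2% |
| Difference seen (SD) | 0.49 / 0.46 / 0.42 | 0.48 / 0.44 / 0.39 |
| Power, no replacement (simulated) | about 42 / 40 / 37% | about 37 / 34 / 30% |
| Power, each arm refilled to 30 | 47 / 45 / 41% | 46 / 43 / 39% |

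With all 30 per arm retained, power for 0.50 SD is only 48%. Sample size limits this inference first, and the exclusions worsen it.

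**The case against.** Section 1 sits in the eligibility paragraph, before randomisation is described, and does not say whether exclusion means withdrawal, non-analysis or replacement. The restriction to vaginal births follows only if the rule is applied after randomisation. That is fair, and it is why the claim is that women *can* be dropped. But failed block is in the same list, and conversion from a trial of labour naturally comes late, so the post-randomisation reading is the more plausible one.

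Differential loss is not shown. The arms differ in one intrathecal dose, share an epidural regimen, and are managed by blinded staff. This stands as a limit on the likely size. Blinding restrains decisions made from knowledge of the allocation; it does not prevent exclusions caused by the drug.

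The illustrated effects are modest, rest on assumed rates, and matter most for secondary outcomes. This also stands. The case for changing the rule does not depend on those figures: the plan permits outcome-related removal of randomised women and does not require it to be disclosed.

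The pain-score filter is a clearer post-randomisation selection for the primary outcome, being explicitly timed after dosing and before T1. True, and it needs the same treatment; it does not excuse the caesarean rule.

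Caesarean itself affects cord gases and Apgar scores, so an all-births comparison is one estimand among several. The plan should state its choice. Dropping caesareans does not, however, give a valid randomised comparison.

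**Conclusion.** The concern holds. On the wording, confidence is high: the caesarean exclusion is not confined to the period before randomisation, and nothing in Section 7 restores the women it removes. Applied as written, it discards complete T0 to T3 data and limits the neonatal and labour comparisons to vaginal births. The oxytocin exclusion is an undefined rule rather than a demonstrated loss.

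The actual size and direction of any bias are unknown. The illustrations assume a normal outcome, the stated selection model, correlations of 0.3 to 0.7 and hypothetical exclusion rates. They give small effects unless the rates differ clearly between arms. The rule should still be changed before analysis, because the outcomes most exposed are those meant to detect harm to the baby.

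**What to change.** - Do not drop randomised women from analysis because of later caesarean or later oxytocin. Analyse all available Doppler, MAP and FHR data from T0 to T3 by allocated group. Women who deliver before T3 contribute the scans they have, with missing scans and reasons reported by arm.
- Limit the oxytocin exclusion to use before randomisation. Scans are taken between contractions and oxytocin may alter uterine activity, so prespecify how scans after oxytocin but before T3 are handled, with the alternative as a sensitivity analysis.
- Report caesarean and oxytocin use by arm. Analyse Apgar scores, cord gases and birth weight for all births. State the denominator for the midwifery rate and how stage durations are treated when labour ends in caesarean (for example, as censored).
- Keep the restricted set as a sensitivity analysis.
- Keep women affected by the pain-score filter, misplaced catheters, failed block and ultrasound non-cooperation, or report their numbers and reasons by arm. Otherwise the set is not fully as randomised.
- State whether 90 counts women randomised or women retained, and whether excluded women are replaced. Section 2 and the pain-score condition in Section 3 need reconciling on this.

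The cost is wording, one by-arm table and the sensitivity analyses. The scans are already scheduled. The downside is collecting routine delivery and neonatal data for these women, and somewhat more heterogeneity.

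### The ultrasound-cooperation exclusion has no time limit, so one unobtainable scan after allocation can remove a randomised woman with all her data

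*Combined protocol and SAP*

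**What the plan says.** Section 1 (Study design) has two exclusion sentences. The first lists conditions known at entry. The second excludes "those who could not cooperate with ultrasound detection" and gives no time point. The same sentence excludes women in whom the block failed ("The patients who were failed to administer combined spinal and epidural block analgesia") and "those who were transferred from vaginal trial labor to cesarean section". The first of these can be known only once the procedure has been attempted, and the second can arise at any time in labour.

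Section 3 (Study intervention) places randomisation before the spinal drug: "At the time of request for labor analgesia, patients were randomized to receive either" one of the three spinal regimens. Section 5 (Primary outcomes) sets the scans at "before analgesia (T_0) and 30 min (T_1), 60min (T_2), 90 min (T_3) after analgesia in the three groups".

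Section 4 (Ultrasonic examination method) gives the scanning conditions: "The patients were placed in a supine position with calm breathing to perform doppler ultrasonography during the interval of contractions". Indexes for three vessels are each measured three times and averaged. Section 3 also expects that pain may return: "Any breakthrough pain was managed with a physician-administered epidural bolus".

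Neither Section 1 nor Section 7 (Statistical Analysis Plan) defines an analysis population, a rule for a missing scan, or a count of exclusions by group.

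**The concern.** An exclusion applied after randomisation for a reason that treatment may influence weakens the comparison that randomisation set up. Being calm and still enough to be scanned at 30, 60 or 90 minutes plausibly depends on comfort, and the three arms receive different spinal drugs. If unscannable women are dropped, the women who remain may be selected differently in each arm.

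The second cost is more certain. The clause excludes the woman, not the scan. A woman who cannot be scanned at T3 could lose valid T0, T1 and T2 values for all nine primary indexes (S/D, PI and RI in three vessels). She would also lose her MAP, FHR, labour times, cord blood gases and Apgar scores, most of which do not need her to cooperate with ultrasound.

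**Working it through.** **Timing.** The plan has no figure to reproduce on this point, so the first check is of sequence.

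1. Randomisation is at the request for analgesia (Section 3).
2. T0 is before analgesia (Section 5). The documents do not say whether the T0 scan comes before or after the allocation is opened.
3. The spinal drug follows, then a VAS check at 15 minutes (Section 3).
4. T1, T2 and T3 follow at 30, 60 and 90 minutes (Section 5).

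So 3 of the 4 scans come after the allocated drug. Nothing in Section 1 confines the cooperation clause to T0, and two neighbouring clauses in its sentence reach past allocation.

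**Illustration of size.** From the documents: 30 women per arm, *P* < 0.05, independent-sample t test between groups. Assumed, because the documents give neither: a fraction q of an arm is lost, being the least cooperative women on a normally distributed trait, and that trait correlates r with the Doppler index.

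Shift in an arm's mean = r × φ(z) / (1 − q), where z is the 1 − q normal quantile and φ the normal density.

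- q = 0.05: r × 0.109
- q = 0.20: r × 0.350
- Difference between the two arms: r × (0.350 − 0.109) = r × 0.241
- r = 0.3 gives 0.072 SD; r = 0.5 gives 0.121 SD

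The standard error should use the women who remain, 30 × 0.80 = 24 and 30 × 0.95 = 28.5, taking an SD of 1 in each arm:

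- SE = √(1/24 + 1/28.5) = 0.277 SD
- Bias/SE = 0.072/0.277 = 0.26 to 0.121/0.277 = 0.44

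Taking the test as two-sided (the plan does not say), a bias of d standard errors with no true difference gives a type I error of 1 − Φ(1.96 − d) + Φ(−1.96 − d). That is 0.058 at d = 0.26 and 0.072 at d = 0.44.

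**Sensitivity.** Suppose one arm loses women and the other loses none, with the same shift formula and allowing for the reduced variance in the depleted arm:

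| Removed from one arm | Shift, r = 0.3 to 0.5 | Type I error |
|---|---|---|
| 1 of 30 | 0.023 to 0.038 SD | 0.051 to 0.053 |
| 3 of 30 | 0.058 to 0.097 SD | 0.056 to 0.066 |
| 6 of 30 | 0.105 to 0.175 SD | 0.067 to 0.101 |

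The distortion is negligible if removals are rare or balanced. It becomes noticeable only if several women are removed and the arms differ.

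**The case against.** The best defence is that the route from arm to exclusion is narrow. Every arm receives the same epidural loading dose and background infusion. Women must have a VAS below 3 at 15 minutes to be included, scans are taken between contractions, and breakthrough pain is treated. Cooperation may well be hardest at T0, when a woman has just asked for pain relief and has had none, and a failure there cannot be caused by the drug. The sonographer is blinded. The clause may have been meant for T0 only.

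Most of this stands as a limit on size. A reader might infer that the spinal drugs produce different restlessness and that the primary results are therefore biased. The documents do not support that: they do not say why women could not cooperate, how many there were, or that arms differed. Nor can a loss of precision be claimed as certain, because the documents do not say whether excluded women are replaced.

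It does not answer the point about the rule itself. The VAS check is a single look at 15 minutes, and pain can return by 30 to 90 minutes. Blinding prevents deliberate selection but not selection caused by a drug's effect. A T0-only intention is not written down. It could also be said that this is one clause of a wider gap, the lack of an as-randomised analysis population. That is fair, but this clause has its own simple correction, and correcting the neighbouring rules would leave it in place.

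**Conclusion.** The point holds as a defect in the rule, not as a demonstrated bias. As written, the exclusion allows a randomised woman to be removed, with all her completed data, because of one scan that failed after allocation, and the reason may be related to her arm. The size of any bias is unknown. The figures of 0.07 to 0.12 SD, or 0.26 to 0.44 of the standard error, rest on an assumed four-fold difference in loss (20% against 5%) and an assumed correlation of 0.3 to 0.5. The documents support neither.

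A reader might also infer that treating a failed scan as missing cures the selection. It does not. Under the planned t tests that woman is still absent from that time point's between-group comparison, and her incomplete pair still drops out of the paired test. What is gained is the rest of her data, analysed as randomised, and a visible count of losses. The change should be made because it is cheap, although the consequence may be small.

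**What to change.** In Section 1, limit this exclusion to the T0 scan and state that T0 is done before the allocation is opened, so that a woman who cannot be scanned then is not randomised. In Section 7, state three things:

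- After allocation, a scan that cannot be obtained is missing for that time point only.
- The woman stays in her randomised group for every other time point and outcome.
- The number of unobtainable scans is reported by arm and time point, and the comparison at an affected time point is read alongside those counts.

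The cost is a sentence or two of text, a fixed order for the T0 scan and the opening of the allocation, and one small table. The downside is some incomplete T1 to T3 series. If enrolment is already complete, the counts can still be reported and women with usable data kept in their randomised groups. No treatment changes.
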